9.4 Non-target lesions

All other lesions (or sites of disease) including any measurable lesions over and above the 5 target lesions should be identified as **non-target lesions** and should also be recorded at baseline. Measurements of these lesions are not required, but the presence, absence, or in rare cases unequivocal progression of each should be noted throughout follow-up.

9.5 Response Criteria

Evaluation of target lesions or serum tumor biomarker

- Complete Response (CR): Disappearance of all target and normalization of serum tumor markers (AFP and beta-hCG) for at least 4 weeks. Any pathological lymph nodes (whether target or non-target) must have reduction in short axis to <10 mm. Complete Response must be confirmed four or more weeks after initial CR is observed.
In patients whose only evidence of disease is elevated serum tumor markers (AFP or beta-hCG), then values must fall below the upper limit of normal for the assay employed and remain at that level for at least 4 weeks.
- Partial Response (PR): At least a 30% decrease in the sum of the diameters of target lesions, taking as reference the baseline sum diameters. This should be present on at least 2 measurements 1 month apart. The serum tumor markers (AFP and beta-hCG) should be stable or decreasing. Partial Response must be confirmed four or more weeks after initial PR is observed.
In patients whose only evidence of disease is elevated serum tumor markers (AFP or beta-hCG), then values must fall $\geq 90\%$ below baseline pretreatment levels for beta-hCG or 50% decrease below baseline pretreatment levels for AFP and persist for 6 weeks. If both tumor markers are elevated and one falls below 90% the other should fall at least below 50% of baseline pretreatment levels.

- Progressive Disease (PD):** At least a 20% increase in the sum of the diameters of target lesions, taking as reference the smallest sum on study (this includes the baseline sum if that is the smallest on study); in addition to the relative increase of 20%, the sum must also demonstrate an absolute increase of at least 5 mm OR the appearance of one or more new lesions OR unequivocal progression of non-target or non-measurable lesions (e.g. worsening bone pain requiring radiation or significant increase in pain medications) OR increase $\geq 50\%$ in serum tumor markers AFP or beta-hCG in 2 samples at least 1 week apart compared to nadir values
- Stable Disease (SD):** Neither sufficient shrinkage to qualify for PR nor sufficient increase to qualify for PD, taking as reference the smallest sum diameters while on study AND/OR stable serum tumor markers, or change that does not qualify as CR, PR or progressive disease. To be assigned a status of stable disease, measurements must have met the stable disease criteria at least once after study entry at a minimum interval (in general, not less than 6-8 weeks).

Evaluation of Non-Target Lesions

- Complete Response (CR):** Disappearance of all non-target lesions and normalization of tumor marker level. All lymph nodes must be non-pathological in size (<10 mm short axis).
- Note: If tumor markers are initially above the upper normal limit, they must normalize for a patient to be considered in complete clinical response.
- Non-CR/Non-PD:** Persistence of one or more non-target lesion(s) and/or maintenance of tumor marker level above the normal limits.
- Progressive Disease (PD):** Appearance of one or more new lesions and/or *unequivocal progression* of existing non-target lesions. *Unequivocal progression* should not normally trump target lesion status. It must be representative of overall disease status change, not a single lesion increase.

Although a clear progression of “non-target” lesions only is exceptional, the opinion of the treating physician should prevail in such circumstances, and the progression status should be confirmed at a later time by the Principal Investigator.

Note: In some circumstances it may be difficult to distinguish residual disease from normal tissue. When the evaluation of complete response depends on this determination, it is recommended that the residual lesion be investigated (fine needle aspirate/biopsy) to confirm the complete response status.

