	
 4. Patients with measurable disease according to RECIST v1.1, or with rising AFP or BHCG above the upper limit of normal on two consecutive determinations if no measurable radiologic disease. 5. Patients with brain metastases are allowed onto the study as long as patients have completed their treatment for brain metastasis, no longer require corticosteroids, and are asymptomatic. Subjects with neurological symptoms should undergo a head CT scan or brain MRI to exclude brain metastasis, at the discretion of the treating physician. 6. Patients with ECOG performance status of 0-2. 7. Adequate organ and marrow function as detailed in the protocol. 8. Patients who are willing and able to comply with the protocol and study procedures including willingness to undergo tumor biopsy for tumor cells before therapy to assess for CD30 status (unless archival tumor tissue from orchiectomy or other previous sample is not obtainable despite efforts to do so and a fresh tumor biopsy is not feasible). 
Main Exclusion Criteria:
 
 1. Patients with pure seminoma. 2. Patients with pure teratoma. 3. Chemotherapy within 2 weeks of initiating study treatment. 4. Major surgery within 3 weeks of starting study treatment. There is no minimum time requirement for minor procedures such as biopsy or vascular access placement. 5. Radiation within 2 weeks of starting study treatment. 6. \geq Grade 3 neuropathy at the time of enrollment. 7. Pregnancy or breast-feeding. 8. Previous treatment with any anti-CD30 directed therapy.

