3. ELIGIBILITY CRITERIA

3.1 Inclusion Criteria

Subject must meet all of the following applicable inclusion criteria to participate in this study:

1. Age \geq 18 years at the time of informed consent.
2. Patients with histologically or serologically confirmed relapsed/refractory non-seminoma germ cell tumor, (i.e., embryonal carcinoma, choriocarcinoma, or yolk sac tumors) including female GCT and primary mediastinal NSGCT.
3. Patients must have progressed after prior high dose chemotherapy (HDCT) treatment, been deemed not to be a candidate for high dose chemotherapy or refused high-dose chemotherapy, and be considered incurable by other standard therapies including further chemotherapy or surgery. There is no maximum allowable number of previous therapies.

“Failure” of prior therapy is defined as:

- a. A >25% increase in the products of perpendicular diameters of measurable tumor masses during prior therapy which are not amenable to surgical resection.
- b. The presence of new tumors which are not amenable to surgical resection.
- c. An increase in AFP or beta-hCG (two separate determinations at least one week apart are required if rising tumor markers are the only evidence of failure).

NOTE: Patients with clinically growing “teratoma” (normal declining tumor markers and radiographic or clinical progression) should be considered for surgery.

4. Patients must have evidence of recurrent or metastatic carcinoma by one or more of the following:
 - i) The appearance of metastatic disease by standard imaging techniques
 - ii) The appearance of rising serum tumor marker, AFP or beta-hCG

- NOTE:** If a rising tumor marker is the only evidence of progressive disease, at least 2 consecutive rising values at least one week apart are needed. Patients with only evidence of disease is rising tumor marker AFP and beta-hCG will be provided alternate causes of increased serum levels of these markers are not present, such as cross reaction with luteinizing Hormone (LH) (that can be tested if needed by testosterone suppression of LH), hepatitis, use of marijuana or second primary tumor, etc.
5. Patients with primary medistinal non seminomatous germ cell tumor are eligible if they have received first line platinum based chemotherapy and their recurrence is not amenable to surgical resection based on the treating physician expert opinion.

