5. TREATMENT PLAN

- Eligible patients will be divided into two cohorts, those who are CD30 positive and those who are CD30 negative/unknown. Both groups will be treated similarly and in parallel but analyzed separately.
- CD30 status may be unknown in the unlikely case of tumor-marker-only relapse or when a fresh tumor biopsy is not feasible, and archival tumor tissue is not obtainable

despite efforts to do so. These patients will be included in the CD30 negative cohort for analysis purposes, since statistically NSGCT are more likely to be CD30 negative.

The number of such patients with unknown CD30 status should not exceed 5 patients.

- Enrollment to the study does not have to wait for determination of CD30 status prior to treatment, unless in the situation where one arm is closed for enrollment or an interim assessment of response for the Simon stage I phase is needed. For example:
 - The first 10 patients can enroll on the study and start on therapy without waiting for CD30 status assessment. Prior to enrolling patient number 11, CD30 status need to be determined for all patients to make sure an interim assessment of response for the Simon stage I phase is not needed (i.e. one arm is at 10 patients).
 - If an arm has closed for lack of efficacy, CD30 status need to be assessed prior to starting therapy to make sure that patients belong to the open arm.
 - If both arms advance to the second stage of the Simon design then enrollment can again be pursued without waiting for CD30 status until one arm is closed to accrual.
- Eligible patients will be treated with brentuximab vedotin at 1.8 mg/kg IV every 3 weeks (maximum dose of 180 mg) indefinitely until disease progression, unacceptable toxicity, or study closure.
- Eligible patients with grade 2 peripheral neuropathy at enrollment will be treated with brentuximab vedotin at 1.2 mg/kg IV every 3 weeks (maximum dose of 180 mg) indefinitely until disease progression, unacceptable toxicity, or study closure.
- Response to treatment will be assessed clinically with history, physical exam and tumor markers measurement (BHCG and AFP) on day 1 of each cycle and with CT scans after cycle 2, 4, and every 4 cycles thereafter while receiving treatment.

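### Marker progression in Section 9.5 has no upper-limit-of-normal or absolute floor, so two rises within the normal range can be PD and cut short PFS and duration of remission

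*Combined protocol and SAP*

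**What the plan says.** Section 9.5 lists several alternative routes to progressive disease, joined by OR. One is a rise of 50% or more "in serum tumor markers AFP or beta-hCG in 2 samples at least 1 week apart compared to nadir values". The text does not say whether both samples must reach the 50% mark.

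Neighbouring rules are built differently:

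- **Lesion progression, same definition:** besides the 20% relative rise, "the sum must also demonstrate an absolute increase of at least 5 mm".
- **Marker-only complete response, Section 9.5:** "then values must fall below the upper limit of normal for the assay employed and remain at that level for at least 4 weeks".
- **Eligibility, synopsis item 4:** without measurable disease, "rising AFP or BHCG above the upper limit of normal on two consecutive determinations". The body criterion, Section 3.1 item 4, asks for consecutive rising values and names no ULN.
- **Other explanations for a rise, Section 3.1:** marker-only patients may enter if "alternate causes of increased serum levels of these markers are not present". The PD rule has no such check.

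Section 5 schedules "tumor markers measurement (BHCG and AFP) on day 1 of each cycle", and a cycle is 21 days.

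Progression is a PFS event (9.9.1, 12.2.2), ends duration of remission (9.9.4), closes the window for best overall response (9.6) and is listed in 6.2 as a reason to leave protocol therapy.

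**The concern.** A relative rise over the lowest value yet seen means little when that value is well inside the normal range, because a small absolute change is then a large percentage. The nadir can only fall and a new sample comes every cycle, so the chance of meeting the rule by noise grows with time on study. Either marker is enough: a patient whose tumour secretes only beta-hCG can be called progressed on a normal AFP.

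The patients most exposed are those who stay on study with normal markers, including those in remission. Their PFS and remission would be recorded as ending without evidence that disease had returned.

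**Working it through.** **1. The plan's own figures.** None depends directly on the marker PD rule. The nearest is the Simon design in 12.3 (stop at 0 of 10; active at 4 or more of 29). It reproduces:

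- Early termination at p = 0.05: 0.95^10 = 0.599 (stated 0.599).
- P(declare active) = Σ over x = 1 to 10 of b(x; 10, p) × P(Bin(19, p) ≥ 4 − x). This gives 0.047 at p = 0.05 and 0.801 at p = 0.20, both as stated.

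**2. Reading the rules together.** Take a nadir of 2 units followed by two samples of 3 units, with an assumed assay ULN above 3. Then 3 / 2 = 1.5, a 50% rise on two samples, so PD is met. All values stayed below the ULN, so the marker part of CR can be met over the same weeks. Nothing in the documents says which prevails.

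**3. How often noise alone would do this.** The documents give no within-patient CV, so it is varied. Assumed model:

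- flat marker, X_j = exp(σZ_j), Z_j independent standard normal, σ² = ln(1 + CV²);
- one sample per cycle;
- false PD when two consecutive samples are each at least 1.5 × the lowest earlier value;
- for two independent markers, risk = 1 − (1 − p)², where p is the one-marker risk. Example, CV 20% and 9 samples: 1 − (1 − 0.276)² = 0.476.

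Five samples run to day 1 of cycle 5 (4 × 21 = 84 days); nine run to day 1 of cycle 9 (8 × 21 = 168 days).

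| Samples | Markers | CV 10% | CV 15% | CV 20% | CV 25% |
|---|---|---|---|---|---|
| 3 | two | 0.03% | 1% | 4% | 8% |
| 5 | one | 0.1% | 2.5% | 9% | 17% |
| 5 | two | 0.2% | 5% | 17% | 31% |
| 9 | one | 0.3% | 9% | 28% | 45% |
| 9 | two | 0.6% | 17% | 48% | 70% |

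Following one marker gives roughly half to two-thirds of the two-marker risk. With a lag-one correlation of 0.5, the 9-sample two-marker figures become about 0.8%, 15%, 41% and a little over 60%. The 5-sample figures fall by more; at CV 20%, from 17% to about 12%.

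If both samples must also exceed a ULN assumed at 3 times the patient's median, the risk is essentially zero (0.012% at most, at CV 40% after 16 cycles).

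**4. Possible reach into ORR.** Suppose a share f of true responders met false PD before confirmation. The response rate counted is then 0.20 × (1 − f). For f = 5, 10 and 20% this is 0.19, 0.18 and 0.16, and power falls from 0.801 to 0.768, 0.730 and 0.640. Here f is purely illustrative: it is not the risk in the table, because responders with elevated, falling markers are not described by a flat-marker model.

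**The case against.** - **Two samples are required.** A reader might infer that any 50% rise is progression. It is not: one isolated high value does not count. The safeguard reduces the problem without removing it, and step 3 already applies it.
- **A relative rule is not unusual in this plan.** Marker PR is a percentage fall, and eligibility in Section 3.1 names no ULN; only the synopsis does. So it would be wrong to say that the plan applies the ULN everywhere except PD. The contrast that stands is with marker CR and with the 5 mm lesion floor. Marker-only PR is less exposed, since it starts from an elevated baseline.
- **The 9-sample horizon may be long.** Section 1.2 cites a median PFS of 4 weeks with single agents, so many patients would give few samples. That is fair, and it is why the 3- and 5-sample rows are shown.
- **The model covers a subset.** It describes patients whose markers are normal at baseline or have normalised. The documents do not give the size of that group.
- **The decision rule is hardly touched.** A reader might infer that the primary result is undermined. Section 9.6 keeps the best response recorded before progression, so a response confirmed before the rise still counts. PFS is estimated by Kaplan-Meier for each cohort, with no test or comparator.
- **Investigators would not call such a rise progression.** Perhaps so, but Section 13.2 requires conduct exactly as written, and unwritten judgement at several open-label sites could date progression differently.

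**Conclusion.** The concern holds in a limited form. As written, a confirmed rise of at least 50% over nadir counts as PD even when every value is normal, so the marker part of CR and PD can both apply. The main effect is on PFS and duration of remission; ORR is exposed only before confirmation. The documents do not support a claim of material power loss in the primary test.

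The size depends on the assumed CV, on flat markers and on how many markers are followed. With both followed, it ranges from negligible at a CV of 10% (0.2% by 5 samples, 0.6% by 9) to substantial at 25% (31% and 70%). The percentages show direction and range; they do not predict this trial. The gap in the rule itself rests on the text alone. It should be corrected, though it does not invalidate the design.

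**What to change.** Add a clause to Section 9.5, limited to the PD used for best overall response, PFS and duration of remission: a marker rise counts only if both samples are at least 50% over nadir and both exceed the assay's ULN. This also settles whether both samples must reach 50%. The plan already uses the ULN for CR, so no new measurement is needed. A minimum absolute rise would be an alternative parallel to the 5 mm floor, but it needs a figure that the documents do not supply.

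There are two costs. True marker progression still inside the normal range would be dated later, by an amount that cannot be estimated from the documents. And because 9.5 holds the only marker-PD definition while 6.2 lists progression as a reason to discontinue, an unrestricted edit would also alter the discontinuation criterion. The sponsor should therefore label the clause as endpoint classification and reconcile it with the CR wording in 9.5 and with 6.2. Whether treatment stops on such a rise is left to the investigators.

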9.6 Evaluation of best overall response

The best overall response is the best response recorded from the start of the treatment until disease progression/recurrence (taking as reference for progressive disease the smallest measurements recorded since the treatment started). In general, the patient's best response assignment will depend on the achievement of both measurement and confirmation criteria. Overall responses for all possible combinations of tumor responses in target and non-target lesions are summarized below

Target Lesions	Non-Target Lesions	New Lesions	Overall Response	Best Overall Response when Confirmation is Required*
CR	CR	No	CR	≥ 4 wks. Confirmation**
CR	Non-CR/ Non-PD	No	PR	≥ 4 wks. Confirmation**
CR	Not evaluated	No	PR	
PR	Non-CR/ Non-PD/ not evaluated	No	PR	
SD	Non-CR/ Non-PD/ not evaluated	No	SD	Documented at least once ≥ 4 wks. from baseline**
PD	Any	Yes or No	PD	no prior SD, PR or CR
Any	PD***	Yes or No	PD	
Any	Any	Yes	PD	

- * See RECIST 1.1 manuscript for further details on what is evidence of a new lesion.
 - ** Only for non-randomized trials with response as primary endpoint.
 - *** In exceptional circumstances, unequivocal progression in non-target lesions may be accepted as disease progression.
- Note: Patients with a global deterioration of health status requiring discontinuation of treatment without objective evidence of disease progression at that time should be reported as “*symptomatic deterioration.*” Every effort should be made to document the objective progression even after discontinuation of treatment.

9.7 Confirmation

The main goal of confirmation of objective response is to avoid overestimating the response rate observed. In cases where confirmation of response is not feasible, it should be made clear when reporting the outcome of such studies that the responses are not confirmed.

To be assigned a status of PR or CR, changes in tumor measurements must be confirmed by repeat assessments that should be performed no less than 4 weeks after the criteria for response are first met. Longer intervals as determined by the study protocol may also be appropriate.

In the case of SD, follow-up measurements must have met the SD criteria at least once after study entry at a minimum interval (in general, not less than 6-8 weeks) that is defined in the study protocol.

9.8 Duration of follow-up:

All patients, including those who discontinue protocol therapy early, will be followed for disease progression, and survival until death. Follow up for disease progression and survival will be every 2 months \pm 2 weeks for the first year from the date of registration, every 4 months \pm 2 weeks during year 2, and every 6 months \pm 4 weeks for years 3-5. Patients who progress will be followed for resolution of all study related toxicity.

9.9 Definitions of Response Evaluation:

9.9.1 Progression-Free Survival Time

Definition: A measurement from the start of the treatment until death or criteria for disease progression are met. Surviving patients without progression are treated as censored at last date known alive.

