
STATISTICAL CONSIDERATIONS
	
a) Definition of primary outcome/endpoint:
 
Objective response rate is the proportion of patients who achieve either a partial or complete response.
 
Complete response is defined as disappearance of all target lesions and normalization of serum tumor markers (AFP and beta-hCG) for at least 4 weeks. Any pathological lymph nodes (whether target or non-target) must have reduction in short axis to <10 mm. Complete Response must be confirmed four or more weeks after initial CR is observed.
 
In patients whose only evidence of disease is elevated serum tumor markers (AFP or beta-hCG), then values must fall below the upper limit of normal for the assay employed and remain at that level for at least 4 weeks.
 
Partial response is defined as at least a 30% decrease in the sum of the diameters of target lesions, taking as reference the baseline sum diameters. This should be present on at least 2 measurements 1 month

apart. The serum tumor markers (AFP and beta-hCG) should be stable or decreasing. Partial Response must be confirmed four or more weeks after initial PR is observed.

In patients whose only evidence of disease is elevated serum tumor markers (AFP or beta-hCG), then values must fall $\geq 90\%$ below baseline pretreatment levels for beta-hCG or 50% decrease below baseline pretreatment levels for AFP and persist for 6 weeks. If both tumor markers are elevated and one falls below 90% the other should fall at least below 50% of baseline pretreatment levels.

b) Definition of secondary outcomes/endpoints:

Progression-free survival (PFS) time is the time measured from the date of initiation of therapy until disease progression or death, whichever comes first. Patients alive and progression-free will be censored at their last follow-up.

Overall survival (OS) is the time measured from the date of initiation of therapy until death, regardless of cause. Patients alive at the time of data analysis will be censored at their last date of contact.

c) Analytic plan for primary objective:

The ORR and its 95% exact CI will be summarized for the total population and by cohort using the F distribution method (Collett 1991).

d) Analytic plan for secondary objectives:

- Both PFS and OS will be estimates using the methods of Kaplan and Meier for each cohort separately.

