2.2.2 Secondary Endpoints

1. Progression-free survival time defined from the start of the treatment until death, criteria for disease progression are met, or last follow-up visit. Overall survival time defined from the start of the treatment until death or last follow-up visit.
2. Toxicity measured by Common Toxicity Criteria 4.0 and need for treatment delay, dose reduction, or early discontinuation.
3. Correlation between tumor CD30 staining intensity/localization and objective response and progression-free survival.

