6.2 Protocol Therapy Discontinuation

In addition to discontinuation from therapy related to toxicities as outlined in Section 6.1, a subject will also be discontinued from protocol therapy and followed up per protocol under the following circumstances:

- Evidence of disease progression
- The treating physician thinks a change of therapy would be in the best interest of the subject
- The subject requests to discontinue protocol therapy, whether due to unacceptable toxicity or for other reasons
- In case a subject decides to prematurely discontinue protocol therapy (“refuses treatment”), the subject should be asked if she or he may still be contacted for further scheduled study assessments. The outcome of that discussion should be documented in both the medical records and in the eCRF.
- A female subject becomes pregnant
- Delays of greater than 4 weeks are prohibited without approval of the Sponsor.

Subjects will be removed from protocol therapy and the site investigator notified when any of the criteria listed above apply. The reason for discontinuation of protocol therapy will be documented on the electronic case report form (eCRF).

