7.4 Long Term Follow-up Evaluations

Patients who achieve a complete remission and are off treatment will be followed every 2 months ± 2 weeks for first year from date of registration. Follow up visits will be done per institutional standard of care. Patients who are discontinued from the treatment for other reasons and are not in remission will be followed for long-term survival and subsequent therapy.

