9.9.2 Overall Survival Time

Definition: A measurement from the start of the treatment until death. Patients surviving are treated as censored at last date known alive.

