12.2.2 Definition of Secondary Endpoints

Progression-free survival (PFS) is the time measured from the date of initiation of therapy until disease progression or death, whichever comes first. Patients alive and progression-free will be censored at their last disease assessment.

Overall survival (OS) is the time measured from the date of initiation of therapy until death, regardless of cause. Patients alive at the time of data analysis will be censored at their last date of contact.

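### PFS censoring is defined in conflicting ways, and Section 9.9.1 applies the overall-survival rule to PFS

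*Combined protocol and SAP*

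**What the plan says.** The combined protocol and SAP states the PFS censoring date in four places:

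- Section 9.9.1: "Surviving patients without progression are treated as censored at last date known alive".
- Section 12.2.2 (Statistical Methods): "Patients alive and progression-free will be censored at their last disease assessment".
- Synopsis, Statistical Considerations, item b: "Patients alive and progression-free will be censored at their last follow-up".
- Section 2.2.2: "Progression-free survival time defined from the start of the treatment until death, criteria for disease progression are met, or last follow-up visit".

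For overall survival, Section 9.9.2 says "Patients surviving are treated as censored at last date known alive", the same date that Section 9.9.1 uses for PFS. Section 12.2.2 keeps the two endpoints apart, with the last assessment for PFS and the last contact for overall survival. Section 12.7.2 names Kaplan-Meier estimation by cohort and refers to none of these definitions. No text gives one section precedence.

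**The concern.** The date a patient was last known alive says nothing about progression. Censoring PFS there treats the interval since the last assessment as progression-free when nobody looked.

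The two dates separate only for patients who are alive, have no recorded progression and are no longer assessed. The protocol makes such patients possible:

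- Section 6.2 allows treatment to stop when "The treating physician thinks a change of therapy would be in the best interest of the subject".
- Section 9.6 describes "Patients with a global deterioration of health status requiring discontinuation of treatment without objective evidence of disease progression at that time".
- Section 7.4 then says "Patients who are discontinued from the treatment for other reasons and are not in remission will be followed for long-term survival and subsequent therapy".
- Footnote 12 of the study calendar makes follow-up markers and imaging conditional on availability.

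Two analysts could therefore draw different PFS curves from the same data, each following the document, and the Section 9.9.1 curve is never the lower one. In a single-arm trial PFS will be read against background figures such as the 4-week median in Section 1.2, so an upward shift flatters the drug.

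**Working it through.** **No plan figure to reproduce.** PFS has no stated sample size, event count, test or threshold. The check covers direction and then size.

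**Direction.** Progressions and deaths are the same events under both rules; only censoring times move. The Kaplan-Meier estimate is the product over event times of (1 − d/n), with d events among n at risk. Later censoring leaves every d unchanged and can only increase n, so each factor stays the same or rises, and so does the curve.

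**Hand example (assumed data).** Take 29 patients. Three are progression-free at a last scan in week 6 and known alive at week 52. The other 26 have events evenly spaced over weeks 3 to 30 (step 27/25 = 1.08 weeks), with 3 events by week 6 and 22 by week 26.

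- Last known alive: nobody is censored before week 26, so PFS is (29 − 22)/29 = 7/29 = 0.24.
- Last assessment: PFS is 26/29 at week 6. The three then leave, 23 remain at risk and 4 are event-free at week 26, so PFS is (26/29) × (4/23) = 0.16.

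With one such patient the values are 0.17 and 0.14; with five, 0.31 and 0.17.

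**Simulation inputs.** There were 200,000 patients per scenario, analysed under both rules, with deaths as events under both.

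- From the documents: markers every 3 weeks; CT at weeks 6, 12 and 24, then every 12 weeks.
- Guided by Section 1.2: median PFS of 4 weeks and overall survival of 4 months give about 17 − 4 = 13 weeks from progression to death. Survival of 8 months gives about 35 − 4, taken as 30 weeks. Subtracting medians is only approximate.
- Assumed: progression medians of 4 to 16 weeks; progression-to-death medians of 13, 26 or 30 weeks; 10, 20 or 30% leaving assessment after week 6 or 12; exponential times; follow-up of 26 to 104 weeks.

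**24-week PFS (%).** Scenarios are progression median / progression-to-death median (weeks) / percent unassessed.

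| Scenario | Last assessment | Last known alive |
|---|---|---|
| 4/13/20% | 3.5 | 4.0 |
| 8/26/20% | 15.7 | 18.1 |
| 8/30/30% | 17.3 | 21.0 |
| 16/30/30% | 38.8 | 43.3 |

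**Range of the 24-week shift (points), by progression median:** 0.28–2.07 (4 weeks), 0.50–3.16 (6), 0.64–3.70 (8), 0.85–4.34 (12), 0.96–4.51 (16). For 4 to 8 weeks the range is 0.41–4.63 if progression needs two consecutive raised assessments, and 0.26–3.80 with CT-only detection. With complete assessment the shift is nil at 24 weeks and at most 0.1 point at 52 weeks.

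**Median PFS.** It moves by less than 0.1 week in the 4- to 8-week base scenarios, by up to 1.3 weeks at a 6-week median under the two-sample rule, and from 18 to 21 weeks in 16/30/30%.

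**Patients affected per 29:** about 0.1 to 1.7 for 4- to 8-week medians, and up to 3.0 at 16 weeks.

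**Against sampling error (6,000 cohorts of 29 per scenario).**

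| Scenario | Mean shift | SD of 24-week PFS | Ratio | Cohorts where the estimates differ |
|---|---|---|---|---|
| 4/13/20% | 0.5 | 3.4 | 0.15 | 16% |
| 8/26/20% | 2.3 | 7.0 | 0.33 | 64% |
| 8/30/30% | 3.7 | 7.3 | 0.51 | 82% |
| 16/30/30% | 4.5 | 9.5 | 0.47 | 96% |

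The Section 9.9.1 estimate was never the lower one in any of the 24,000 cohorts.

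**Sensitivity to the model.** With CT-only detection, a 12-week progression-to-death median, assessment stopping at a random time before the event and follow-up of 52 to 104 weeks, the average shift at 12 or 26 weeks stayed below 1 point. Most unassessed patients then die and count as events under either rule.

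**The case against.** The case for giving this little weight is substantial.

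- **Progression follow-up is planned for everyone.** Section 9.8 and footnote 10 of the study calendar follow progression and survival on one schedule, and Section 9.6 asks for every effort to document progression after treatment stops. If this is done, the two dates nearly coincide. This stands as to size, but footnote 12 concedes that the data will sometimes be missing.
- **Section 7.4 is weak evidence of a large unassessed group.** It does not say that only survival is followed, and patients not in remission include those who have already progressed. This also stands.
- **The documents' own figures imply a small effect.** With a 4-week progression median and 13 weeks to death, 10 to 30% unassessed gives roughly a quarter to three quarters of a point, 0.1 to 0.3 affected patients per 29, and no change in the median. The larger shifts need longer post-progression survival or slower progression.
- **The 18 versus 21 week median is one step of the 3-week marker schedule,** at a progression median that the documents do not give. The share of cohorts that differ counts any difference, however small.
- **An analyst would probably use Section 12.2.2,** which sits beside the analysis plan, and the synopsis and Section 2.2.2 wording can be read to agree with it. That is plausible, but it is inference and not a stated rule.

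These points limit the weight. None removes the contradiction between Sections 9.9.1 and 12.2.2.

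**Conclusion.** The plan is wrong as written in Section 9.9.1. It sets a contact-based censoring date for PFS, contradicts Section 12.2.2, and has no precedence rule. The direction of the error is certain: the Section 9.9.1 curve is equal or higher.

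The size is uncertain and probably modest: 0.3 to 3.7 points at 24 weeks for progression medians of 4 to 8 weeks in the base model, and under 1 point with the 4-week PFS and 4-month survival figures of Section 1.2. All of this rests on an assumed 10 to 30% of patients leaving assessment. In the four cohort scenarios the mean shift was at most about half a sampling SD. PFS is a secondary endpoint without a test, and the response-rate decision rule is not affected. No effect on the exploratory CD30 proportional hazards model is claimed.

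**What to change.** Put the Section 12.2.2 rule, censoring at the last disease assessment without progression, into the synopsis, Section 2.2.2 and Section 9.9.1. Keep the last-contact or last-known-alive date for overall survival only. State which assessments count as a disease assessment, since markers and examination occur every cycle and CT less often.

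Separately, reconcile Sections 7.4 and 9.8 on progression follow-up after treatment stops. The censoring correction does not depend on this.

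The cost is wording in three definitions, and reported PFS may be slightly lower. Reconciling Sections 7.4 and 9.8 may add assessments, depending on which text is kept.

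The change removes only part of the bias from missed assessments, because an unrecorded progression followed by death still counts as a later event. With an 8-week progression median, complete assessment gives 12.5% at 24 weeks. From the rounded figures, the share of bias remaining is (15.7 − 12.5)/(18.1 − 12.5) = 57% in 8/26/20% and (17.3 − 12.5)/(21.0 − 12.5) = 56% in 8/30/30%.
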